## 11. Data Management

All data management, including the design of the CRFs, design of the database, as well as data entry and assurance of data integrity will be assumed by the Investigators or delegates. The CRFs, if possible, will be appended to a participant's clinical chart for direct documentation by the treating physician(s) and nurses. This plan is to accommodate data collection and transcription in the context of limited resources during this outbreak.

## 12. Premature Discontinuation of Treatment

Participants may withdraw from the study at any time for any reason without jeopardy to their current or future care. The investigator may also withdraw patients from the study without the participant's permission in the event of intercurrent illness, adverse events, treatment failures, protocol violation, administrative reasons, or any other reasons. The reason for withdrawal should be clearly documented in the CRF.

Specific criteria for premature discontinuation of treatment will also include, progression of disease due to IFN  $\beta$ -1a or grade IV adverse events felt to be due to IFN  $\beta$ -1a. If the reason for removal of a patient from the study is an adverse event or abnormal laboratory result, the

principal specific event or test will be documented completely on the CRF. A participant will be withdrawn if at any time, in the opinion of the investigator, study participation would not be in the best interest of the participant.

Participants may withdraw or be withdrawn from treatment and this will not automatically lead to withdrawal from the rest of the study. These participants would continue to be followed per protocol for safety and disease course, off therapy. Unnecessary withdrawal of patients should be avoided.

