### 6.5 Follow-up

Collection from daily recordings will be undertaken either prospectively or retrospectively to assess adverse event and efficacy of therapy from day 1 (1st day of treatment) to day 10 and then weekly while admitted to the treatment centre and then 30 days post last dose. For patients for whom therapy is discontinued prior to day 10, assessments will follow the same schedule to allow comparison of disease course.

The following will be recorded, as permitted, starting immediately prior to the onset of administration of IFN  $\beta$ -1a, then on a daily basis whilst the patient is in the treatment centre:

- Temperature; fever will be defined as a temperature  $\geq 38$  °C.
- Concurrent illness symptoms: chills, myalgia, cough, sore throat, nausea, vomiting, diarrhea, hemaorrhage.
- Adverse events will be recorded per protocol. Medication history at baseline and daily will be recorded.
  - Blood samples:
    - 20 cc of Blood for virologic measurement (if feasible).
    - A convalescent serum (10 cc tiger top tube) will be obtained at 1 month (when possible).
  - Survival

Of note, it is expected that there will be missing data points for study participants depending on the clinical care data available in the medical chart and residual blood samples available for testing.

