### **Termination classification**

The investigator will classify the termination status of each participant at the end of the study in the termination page of the CRF according to the following:

- Serious Adverse Event
- Other Adverse Event
- Non-compliance with protocol
- Lost to follow-up
- Voluntary withdrawal not for an Adverse Event
- Withdrawal by Investigator with rationale

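### Section 12 lets the investigator end study participation, not only treatment, for reasons tied to outcome, and guarantees continued follow-up only to patients withdrawn from treatment

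*Protocol*

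**What the plan says.** Section 12 of the protocol is headed as dealing with premature discontinuation of treatment, but it covers two different acts.

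- **Leaving the study.** "The investigator may also withdraw patients from the study", without the patient's permission, for "intercurrent illness, adverse events, treatment failures, protocol violation, administrative reasons" or any other reason. Treatment failure is not defined. The section also speaks of removal from the study for an adverse event or abnormal laboratory result, in which case that event must be fully documented on the case report form. It further requires withdrawal whenever the investigator judges participation not to be in the patient's best interest.
- **Leaving treatment.** "Participants may withdraw or be withdrawn from treatment and this will not automatically lead to withdrawal from the rest of the study". The next sentence gives the guarantee: "These participants would continue to be followed per protocol for safety and disease course, off therapy". The section then adds: "Unnecessary withdrawal of patients should be avoided".

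Section 6.5 supports the second act: "For patients for whom therapy is discontinued prior to day 10, assessments will follow the same schedule to allow comparison of disease course". The paragraph of Section 12 on follow-up of discontinuation leaves follow-up after an adverse event to the investigator's judgement. If the event is related to the drug, this runs until it resolves or is established as chronic. That paragraph repeats that patients taken off the product may continue to be followed and to give specimens. Section 8.3 has serious adverse events collected for 30 days after the last dose, and deaths on therapy or within that window reported.

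**The concern.** The primary endpoint (Section 9.1) is reduction or clearance of viral RNA from day 1 to day 10 and time until virus is undetectable. A patient whose virus does not clear could be called a treatment failure, and that is a listed ground for ending study participation. The sentences that keep follow-up going are tied to stopping the drug, so a patient withdrawn from the study has no clear guarantee of further assessment.

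The design makes this one-sided. The trial is single-arm, and the comparison patients come from retrospective records of people outside the trial (Section 5). Investigator withdrawal under Section 12 can therefore occur only in the treated group. What could be lost:

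- later viral loads;
- symptom data for the repeated-measures analysis;
- non-serious adverse events within the 7 days after the last injection (Section 9.2);
- follow-up time in the Kaplan-Meier and Cox analyses (Section 10.2), if patients are censored at withdrawal.

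Under Section 16, safety and a possible trend toward efficacy against standard of care decide whether the pilot is extended to 100 participants. A modest distortion in 30 to 50 patients could affect that decision.

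**Working it through.** The protocol gives no withdrawal rate, expected clearance rate or sample size calculation, so there is no figure of its own to reproduce. The check is first textual, then illustrative.

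**1. Which text protects a patient withdrawn from the study?**

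- The Section 12 guarantee and Section 6.5 both apply when treatment is stopped. Neither mentions withdrawal from the study.
- The Section 12 paragraph on follow-up of discontinuation does cover patients who withdraw for an adverse event, and is not limited to treatment withdrawal. But it provides follow-up as the investigator sees fit, not the protocol schedule, and says nothing on treatment failure.
- Section 8.3 does not depend on study status, but covers only serious adverse events and deaths. Even if the last dose were on day 1, its window would reach day 31. It therefore spans the 2-week and 1-month survival rates of Section 10.2, if these are counted from the first dose.

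The gap is thus later viral load, symptoms and non-serious adverse events. Vital status is exposed only if the reporting rule is not followed or patients are censored at withdrawal.

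**2. Illustration for clearance.** Assumptions not in the protocol: true clearance 50%, *w* failures withdrawn, and these patients dropped from the denominator. Recorded clearance = 0.5*n*/(*n* − *w*), with *n* = 30 and 50 from Section 10.1.

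- *n* = 30: *w* = 3 gives 15/27 = 56%; *w* = 5 gives 15/25 = 60%.
- *n* = 50: *w* = 3 gives 25/47 = 53%; *w* = 5 gives 25/45 = 56%.
- If the same patients are kept as not cleared: 15/30 = 25/50 = 50%, no shift.

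**3. Illustration for mortality.** The fatality range of 57-90% is from Section 1.1. Assumption: *k* patients who would die are withdrawn, their deaths are not captured, and they leave the denominator. Recorded mortality = (*D* − *k*)/(*N* − *k*).

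- 57%, *N* = 30, *D* = 17: 56.7% at *k* = 0; 14/27 = 51.9% at *k* = 3; 12/25 = 48.0% at *k* = 5.
- 57%, *N* = 50, *D* = 28 (28.5 taken as 28): 56.0%; 25/47 = 53.2%; 23/45 = 51.1%.
- 90%, *k* = 5: 22/25 = 88.0% for *N* = 30 and 40/45 = 88.9% for *N* = 50, against 90.0% in both.
- Deaths captured under Section 8.3 and all treated patients analysed: no shift.

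**The case against.** The strongest reply is that a reader might infer from Section 12 that bad outcomes are removed from the data, and the protocol does not say that.

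- No section excludes withdrawn patients from an analysis. The analysis set may be settled in a statistical analysis plan that is not at hand. The clearance figures above depend on a denominator that the protocol does not prescribe.
- Adverse events are not simply lost. The event that prompts removal is documented, and serious events and deaths remain reportable.
- Section 9.1 scores any virus-positive sample as positive on that day, so a patient judged a virologic failure would normally already have positive results on record.
- The termination page, with categories such as "Non-compliance with protocol", does not show data removal. It classifies status at the end of the study, does not list treatment failure, and makes withdrawals traceable.
- A patient withdrawn for an adverse event, protocol violation or administrative reason need not be a virologic failure, so bias in favour of the drug cannot be asserted for every ground.
- The protocol discourages unnecessary withdrawal and already expects missing data, with blood sampling only where feasible.

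All of this stands, and it narrows the point to follow-up after withdrawal. It does not remove it. The discouragement leaves the listed grounds in force. Missing data that depend on outcome differ in kind from data missing because a sample could not be taken. An analysis plan can decide how to treat missing viral loads, but cannot recover ones never collected. Who continues to be followed is fixed by the protocol.

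**Conclusion.** The point holds as a risk of informative loss of follow-up in the treated group, created by wording that does not separate leaving the study from leaving treatment. Most exposed are later viral loads, symptoms and non-serious adverse events. Survival and serious adverse events are less exposed, and not at all if the 30-day reporting rule is followed and all treated patients are analysed. The direction tends to favour the drug for the treatment-failure ground and is otherwise uncertain.

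The size cannot be derived from the protocol. In the illustration for clearance the shift is 3 to 10 percentage points, resting wholly on the assumed 50% clearance, the assumed 3 to 5 withdrawals and the assumed removal from the denominator. This should be corrected because it touches the primary endpoint and the correction is nearly free.

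**What to change.** Reword Section 12 so that it states the following.

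- Withdrawal initiated by the investigator, on any listed ground, does not end data collection. This must include the administrative and catch-all reasons and the best-interest clause; otherwise the gap reopens through them.
- Only the patient's, or substitute decision maker's, withdrawal of consent ends data collection.
- All treated patients are followed on the existing Section 6.5 schedule, as feasible, for viral load, adverse events and vital status to 30 days after the last dose, and are kept in the analysis.

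The rules for reducing or stopping the study drug stay as they are; the change concerns data collection only. The paragraph on follow-up of discontinuation and the termination page should be aligned with it, so that the end of treatment and the end of data collection are recorded separately. The cost is a short amendment and slightly more follow-up of patients off treatment, using assessments already planned.

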### **Lost to follow-up procedures**

In the case of participants who fail to present for a follow-up examination, documented reasonable effort (i.e.; documented phone calls or certified mail) should be undertaken to locate or recall them or at least to determine their health status while fully respecting the participant's rights. These efforts should be documented in the participant's source documents and CRF.

### **Termination classification**

The investigator will classify the termination status of each participant at the end of the study in the termination page of the CRF according to the following:

- Serious Adverse Event
- Other Adverse Event
- Non-compliance with protocol
- Lost to follow-up
- Voluntary withdrawal not for an Adverse Event
- Withdrawal by Investigator with rationale

### **Follow-up of discontinuation**

Participants who withdraw for an adverse event related to IFN  $\beta$ -1a should be followed as deemed appropriate by the investigator until resolution of the event or until chronicity of the event has been established. In cases where the adverse event is not related to IFN  $\beta$ -1a, the participant should be followed as deemed appropriate by the investigator. Documentation is deemed as that in the source documents and as indicated in the CRF. In the event of a loss to follow-up, the loss to follow-up procedures will be followed. As noted above, participants may be withdrawn from investigational product therapy but continue to be followed according to protocol for their clinical course and/or by providing additional blood and respiratory secretion specimens for research testing.

### **Interruption of the study**

The study may be discontinued for administrative reasons or if new data about the investigational product resulting from this or other studies become available, and/or on advice of the regulatory authorities. If the trial is prematurely terminated for any reason, the investigator should inform the study participants in a timely fashion and should assure appropriate therapy and follow-up.

### **Modifications of the study protocol**

No amendments to this study will be made without consultation with, and agreement of, the study sponsors, including the manufacturer of the IFN  $\beta$ -1a i.e. BiogenIdec, Inc. Any

amendment to the study that appears necessary during the course of the study must be discussed by the investigator/physician and the sponsor-investigator concurrently. If there is a need for an amendment, it will become a formal part of the protocol and will undergo appropriate approvals (regulatory authorities). An amendment may be implemented prior to regulatory approval in the event that it is necessary to eliminate apparent immediate hazards to the participants.

An administrative change to the protocol is one that modifies administrative and logistical aspects of a protocol but does not affect the participants' safety, the objectives of the study and its progress. An administrative change can be sent as a notification, as it does not require approval by the Guinean Ministry of Health prior to implementation.

### **13. Conduct of the Investigation**

This study will be conducted in accordance with the Declaration of Helsinki, as well as the International Conference on Harmonization (ICH) Good Clinical Practices (GCP), applicable national and local requirements by the respective authorities (Regulatory Agencies such as Health Protection Branch in Canada; REB/IRB). The investigators will be familiar with the principles elaborated in the Declaration of Helsinki and will adhere to these principles, as well as the GCP guidelines and other local and regional applicable legislations and regulations (e.g. privacy legislation).

### **14. Ethics Review and Consent**

The study and the appropriate documents (protocol, informed consent, product monograph, subject recruitment tools, and any other written information to be provided to the participants) will be reviewed by an REB/IEC of record for each respective treatment centre planning to conduct the study. Before inclusion of the first participant at the site, the study must be approved by, or receive a favorable opinion from, the appropriate REB/IEC. A sample consent form can be found in the application.

Each investigator is responsible for obtaining this approval, or favorable opinion, before the start of the trial and with any subsequent amendment in compliance with Good Clinical Practice (GCP) and local regulations. Copies of these approvals, along with information on the type, version number, and date of the document(s), and the date of approval, must be forwarded to the sponsor-investigator, or delegate. All SAEs occurring during the trial will be reported to the REB/IEC, according to the local REB/IEC policy by the site investigator, as well as to the sponsor (see Safety reporting section of the protocol).

### **15. Time Frame for the Study**

Given the nature of this EBOV outbreak, it is difficult to predict the waves and the study may span more than one wave, and thus it is difficult to determine the actual time to complete the study.

Since this is a pilot study, it is important to have such a protocol in readiness so that, new cases can be immediately enrolled. It is estimated that during a wave, it will be possible to recruit 30 participants, in less than one month. It is planned to propose the study to be conducted at other treatment centres across West Africa. The rationale is to increase the rate of enrolment for the pilot study so that if a potential benefit is detected early, IFN  $\beta$ -1a therapy can be evaluated

relatively rapidly, in an effort to make it available, through the extended study (and possibly a larger multicentre international study) as part of the treatment armamentarium as early as possible.

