### **2.3.2 Procedures to Minimize Risks**

Alcohol swabbing of the skin prior to venipuncture and IFN  $\beta$ -1a injection, and use of sterile disposable needles and syringes will minimize the risk of infection. Applying pressure over needle puncture sites to minimize bruising should also be carried out. Exclusion of patients who have previously experienced a severe allergic reaction to IFN  $\beta$  preparations, and since participants will probably remain in the treatment centres for the duration of treatment, trained personnel will be available in case for allergic reactions post-injection.

For the first ten (10) ebola-infected subjects to receive IFN  $\beta$ -1a, a staggered administration schedule will be used to minimize the effect of any unforeseen serious adverse events in this patient population. The second patient will not be administered IFN  $\beta$ -1a until the first subject has received five (5) doses. Likewise, the third subject will not be administered IFN  $\beta$ -1a until the second subject has received 5 doses. If, in the opinion of the treating physician and the Special Access Program in Conakry, Guinea, no unforeseen serious adverse events are observed five (5) days after the tenth subject has received IFN  $\beta$ -1a, more than one of the remaining

subjects enrolled/to be enrolled in the study may receive their first dose of IFN  $\beta$ -1a on the same day.

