### **5. Study Design**

This study is single-arm clinical trial with a pre- and post- study design. The study will include patients who are admitted with EBOV infection to a treatment centre. If a patient meets the inclusion criteria and gives informed consent (or informed consent is given by a substitute decision maker who is responsible for the patient due to the patient's illness), the patient will be enrolled into the study i.e. the first 30-50 eligible patients will be enrolled. Patients who receive IFN  $\beta$ -1a will be treated through the Special Access/Compassionate Release Program (consent to treatment through their treating physician) administered in Conakry, Guinea. This part of the study will collect data retrospectively, including results from research testing of (residual/to be discarded) blood samples. The study team can make available the systematic data collection forms to the treating physician to help in monitoring of adverse events and effect of therapy, enabling more specific reporting to the Special Access Program administered in Conakry, Guinea by the treating physician for patients receiving IFN  $\beta$ -1a.

As noted above, retrospective data collection will include patients with EBOV disease who do not participate in this clinical trial. Data from IFN  $\beta$ -1a-treated patients will be matched with data from patients who did not receive IFN  $\beta$ -1a, based on age, sex, estimated days post-onset of symptoms, and viral load (if available). This data collection is similar to that proposed in this protocol. Also, this protocol proposes to test blood collected clinically (residual or to be discarded) for comparisons between the groups in this interventional study.

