### **6.2 Initial Evaluation and Baseline Investigations:**

Once the informed consent is signed, and prior to initiation of therapy, eligibility will be confirmed. Some of the data (e.g. demographics) may be collected retrospectively from the patients' chart (source document). Demographics will be collected, the participant will undergo evaluation to review the medical history (will be recorded from the chart and/or obtained from the participant or family members) and a physical examination will be performed by a study physician or one of the treating physicians (chart). These will be recorded in the case report form. The patient's current clinical status will also be documented.

Pre-study screening and baseline investigations will occur, preferably on the same day as signature of the Informed Consent, but definitely prior to initiation of treatment with IFN  $\beta$ -1a, and will be stated as performed on day 1 of hospitalization and day 'X' of illness. Follow-up data will also be recorded on this basis for comparison between relevant time points amongst participants (treated or not with IFN  $\beta$ -1a). It is expected that most eligible participants will be treated within 24 hours of being admitted to the treatment centre. Earlier therapy with IFN  $\beta$ -1a in the course of disease of the illness is likely to offer the highest chance of potential benefits to prevent further deterioration. Days 1-10 mentioned with each of the investigations noted below refer to the days of IFN  $\beta$ -1a therapy and/or follow-up while in hospital. Patients discharged prior to 10 days from initiation of therapy will, if possible, be seen for medical and study follow-up at 1 month post-initiation of treatment. Every effort will be made to combine clinical care follow-up with study follow-up.

Data available in the medical chart will be collected.

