## 10. Biostatistical Considerations

### 10.1 Sample size estimate

There is no expected sample size for this pilot clinical trial as it is to prove feasibility. This study can include any patient who is suspected or proven to be infected with EBOV and has been admitted to the treatment centre. A sample size of 30-50 has been chosen to assess feasibility of running a clinical trial in the setting with a large number of patients and also the feasibility of treating a large number of patients. If successful, a larger clinical trial may be feasible.

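### On the natural reading of the stagger in section 2.3.2, at most 6 to 8 patients can be dosed in the first 30 days, so section 15's estimate of 30 in under a month cannot apply to the wave in which the trial starts

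*Protocol*

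**What the plan says.** Section 15 explains that a protocol should be ready so that "new cases can be immediately enrolled", and estimates that in a wave "it will be possible to recruit 30 participants, in less than one month". It does not mention any stagger.

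Section 2.3.2 introduces a staggered schedule with the words "For the first ten (10) ebola-infected subjects to receive IFN" beta-1a. The second subject may not be dosed "until the first subject has received five (5) doses", and the third waits in the same way for the second. Subjects 4 to 10 are not mentioned one by one. More than one first dose on a day is allowed only if no unforeseen serious adverse event has been seen five days after the tenth subject received the drug.

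Four other places bear on this:
- Section 5 calls the design single-arm and says "the first 30-50 eligible patients will be enrolled". Untreated comparators are matched "based on age, sex, estimated days post-onset of symptoms, and viral load (if available"; the Synopsis adds similar symptoms.
- Section 5.3 requires symptom onset less than 4 days earlier.
- Section 6.2 states: "It is expected that most eligible participants will be treated within 24 hours of being admitted to the treatment centre".
- Section 10.1 justifies the size by feasibility: "A sample size of 30-50 has been chosen to assess feasibility of running a clinical trial".

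**The concern.** Sections 2.3.2 and 15 describe the same opening weeks of the trial and cannot both hold there if the five-dose gap runs through all ten subjects. Section 15 gives the protocol's only accrual figure, in a study whose size rests on feasibility, so that figure should reflect the trial's own safety rule.

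Two practical matters follow.
- **Blocked slots.** Section 2.3.2 does not say what opens the next slot if a subject dies or stops before dose five. Section 1.1 cites fatality of 57-90% for this virus, and sections 6.3, 8.2 and 12 allow early stopping, so this is likely to arise. Read literally, the next subject is then blocked. If sites improvise, the safety rule is weakened.
- **Comparators.** While the stagger lasts, some eligible patients may go undosed only because no slot is open. They share centre, calendar time and eligibility with the treated patients. The planned matching uses none of these three, so it gives such patients no preference over other untreated patients. The comparison is not randomised, and section 16 makes a trend against standard of care one factor in deciding on extension.

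**Working it through.** **Inputs.** Ten staggered subjects, a gap of five doses, and release five days after the tenth subject (section 2.3.2). Daily dosing (Synopsis). Thirty recruits in under a month (section 15). Release is counted from the tenth subject's first dose, which is the earliest reading.

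**All-ten reading.** If the gap between first doses is g days, subject k starts on day 1 + (k - 1)g. With daily dosing, g = 4 if the next subject may start on the day of the previous one's fifth dose, and g = 5 if on the day after. Each earlier subject is assumed to reach dose five, and an eligible patient is assumed to be available for every slot.

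| | g = 4 | g = 5 |
|---|---|---|
| First doses by day 30 | days 1, 5, 9, 13, 17, 21, 25, 29: 8 | days 1, 6, 11, 16, 21, 26: 6 |
| Tenth start | 1 + 9 x 4 = day 37 | 1 + 9 x 5 = day 46 |
| Same-day starts open | 37 + 5 = day 42 | 46 + 5 = day 51 |
| Earliest 30th start | day 42 | day 51 |

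The last row lets everyone remaining start on the opening day. Even if one patient a day may start between the tenth and the opening, only 4 more are dosed (14 in all), so the 30th still waits for the opening. Section 15's figure of 30 is therefore not reproduced: 6 to 8 is 20% to 27% of it. For the opening to fall by day 30, 1 + 9g + 5 <= 30 is needed, so g <= 24/9, about 2.7 days.

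**Narrow reading.** If the gap binds only subjects 1 to 3 and the others start one a day, starts fall on days 1, 5, 9, 10, ..., 16 or on days 1, 6, 11, 12, ..., 18. Same-day starts open on day 16 + 5 = 21 or 18 + 5 = 23, with 14 already dosed. Reaching 30 by day 30 then needs (30 - 14)/10 = 1.6 or (30 - 14)/8 = 2.0 starts a day. That is possible.

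**Duration.** The earliest last visit for 30 patients is the 30th start plus 9 days to the tenth dose plus 30 days of follow-up: 42 + 39 = day 81, or 51 + 39 = day 90. At one start a day, the 30th start falls between day 37 + 20 = 57 (continuing straight after the tenth) and day 51 + 20 = 71 (resuming the day after opening). The last visit is then day 96 to 110. All of these fit within four months.

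**Undosed eligible patients.** The protocol gives no daily arrival rate. If section 15's estimate is taken as one eligible arrival a day, 37 - 10 = 27 to 46 - 10 = 36 would be undosed when the tenth starts. If arrivals are as sparse as the gap, there would be none.

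**The case against.** **Section 15 is an estimate, not a schedule.** It says the study may span more than one wave and that completion time is hard to determine, and its figure refers to a wave in general. That stands as to weight. But the estimate carries no exception for the wave in which the trial starts.

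**Recruiting is not dosing.** The Synopsis describes patients given either interferon or supportive care alone, and section 6.2 speaks of participants treated or not. However, section 5 makes the trial single-arm with comparators collected retrospectively, and the limit of under 4 days since onset rules out enrolling now and dosing weeks later. In effect, recruiting here means dosing.

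**More centres could be added.** The rule counts the first ten subjects to receive the drug and has no per-site exception, so adding centres does not shorten it.

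**The conflict is conditional.** This stands. It needs the all-ten reading and every earlier subject reaching dose five. If a death frees the slot, more than 8 could be dosed.

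**The comparator preference is a matter for the analysis plan.** In part it is. But a log of patients who found no slot open must be kept prospectively. It could not be rebuilt reliably from charts in which section 5 itself expects missing data.

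A reader might also infer three stronger things that the protocol does not support:
- That section 6.2's 24-hour expectation is contradicted at every arrival rate. It can be read as the delay among patients taken into the study. A patient given an open slot can meet it, and 30 - 10 = 20 to 50 - 10 = 40 of the planned patients start after the staggered ten.
- That a slow first month would fail the pilot. Neither section 10.1 nor section 16 has a criterion based on accrual rate.
- That undosed eligible patients are shut out of the comparison. Section 5 admits any patient with the disease who did not receive the drug; it only gives these patients no preference.

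**Conclusion.** The point holds in conditional form. With the five-dose gap applied to all ten subjects and each earlier subject reaching dose five, at most 6 to 8 patients can be dosed in the first 30 days. The tenth start comes no earlier than day 37 to 46, and the 30th no earlier than day 42 to 51. Section 15's estimate therefore cannot apply to the starting wave.

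The all-ten reading is the natural one: the schedule is introduced for ten subjects, two steps illustrate it, and release is tied to the tenth. It is not spelled out, however, and on the narrow reading there is no firm conflict. That the same text gives an opening at day 21 to 23 or at day 42 to 51 is reason enough to clarify a safety rule.

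The day counts are best-case bounds, not expected dates. The consequence is moderate: one stated figure is wrong for the opening period, the slot rule has a real gap, and a source of closer comparators is not secured.

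**What to change.** - **Section 2.3.2:** state that the five-dose gap covers all ten subjects, and what opens the next slot if a subject dies or stops before dose five.
- **Section 15:** say that 30 a month applies only after the stagger ends. Give at most 6 to 8 in the first 30 days and a 30th start no earlier than day 42 to 51, labelled as best-case bounds that assume each subject reaches dose five.
- **Section 5:** during the stagger, give each open slot to the next consecutive eligible consenting patient. This also limits selection, since section 5 otherwise lets the treating physician choose whom to treat.
- **Log:** keep a simple prospective list of eligible patients who arrive with no slot open, with the date eligibility was met. Use them as the preferred concurrent comparators within the matching already planned.

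The cost is a small logging burden and a less favourable stated accrual. The safety stagger and the four-month duration are unchanged.
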